## **5.9 Social Worker Responsibilities**

Responsibilities of interventionist social worker (ISW) are as follows:

- a. The ISW will assist in the development of educational material and scripts for the intervention
- b. The ISW will participate in all design consultation team sessions aimed at refining the modules for the intervention
- c. The ISW will edit and review modified versions of the study intervention after feedback from the design consultation team is obtained.
- d. The ISW will participate in post design consultation forums for finalization of the study intervention
- e. The ISW will participate in all pre-intervention training associated with the intervention, including (and not limited to): training on medication side effects, simulation sessions for scripted material, review of all educational material, use of Zoom (or other teleconferencing platform for consultation)
- f. The ISW will deliver the intervention as configured including: pre-telephone call documentation, study-telephone call, telephonic transmission of visual educational aids (when applicable), post-telephone call documentation (including use of SW-based techniques). The ISW will also be called to use their discretion in employing SW-based techniques for individual patients. All techniques used during the interaction must be documented as part of the study fidelity worksheet to be provided to the ISW by the study team
- g. The ISW will answer questions posed by study participants to the best of their ability. Any questions that cannot be answered, and deemed outside their scope of practice by the ISW as part of the intervention will be documented and sent on to the study investigator for resolution. The ISW is specifically instructed not to answer detailed questions on:
  - a. CVD medication interactions with current medications

- b. Medical issues not directly related with CVD primary prevention related topics (hypertension, hyperlipidemia, diabetes, smoking cessation etc)
- c. Medication dosing, up-titration or down-titration
- d. Referrals to specialty providers with the exception of mental health practitioners
- e. Medications or supplements not-approved by the US Food and Drug Administration
- f. Other questions by the ISW's determination is outside the scope of routine social work practice
- h. This documentation and transmission to the study investigator should be conducted as soon as possible, but no later than 24 hours after completion of the phone call. Notification will be conducted ideally via institutional e-mail or MyChart messaging. The study investigator will be expected to give a response to such questions within 48 hours of receipt.
- i. The ISW will communicate all concerns about logistics of the study to the study coordinator in a timely manner
- j. The ISW will report all potential adverse events to the study team (study coordinator and study PI) as soon as they are aware as delineated in Section 7.2.

The following documents will be provided to the ISW by the study team prior to study launch:

- a. Telephone call intake forms
- b. Educational material associated with module administration
- c. Baseline assessment data for individual participants including participant's learning preferences
- d. Current contact information (phone and e-mail) of the study PI and the study coordinator
- e. A cell phone for the execution of study phone call with SMS transmission capability and associated data
- f. List of CVD-related community resources in Raleigh-Durham Metropolitan area
- g. Resource document with side effect profiles of major classes of medication used in cardiovascular disease primary prevention.
- h.

#### **5.10 Post study intervention**

Participants will be followed after the 24-week intervention at 48 (6-month post intervention) and 72 weeks (1 year post intervention) to assess the durability of the intervention's impact. At those visits, we will collect blood pressures, anthropomorphic and lipid panels similar to the first two study visits. We will also conduct patient-reported data on the durability of the intervention using formal assessment tools for heart-healthy behaviors at each visit.

#### **5.11 Post Intervention Interviews**

After the 6 month intervention is complete, we will approach a convenience sample of 10 participants to participate in an additional key informant interview. All interviews will be completed between the end of the intervention and the participants 12 month visit. These interviews will take place at the participants 6 month visit or by phone at a mutually agreed upon time. Questions will address the participants perception of the intervention's characteristics and program outcomes. All interviews will take approximately 30 minutes and audio recordings using an encrypted recorder if participant agrees to be recorded, will later be transcribed using a

Duke-approved transcription service (rev.com) to transcribe the audio files. Audio recordings will be destroyed after results of study are published. An interview information sheet will be shared with participants asked to participate in interview. They will be verbally consented to participate or decline if they choose. Participants who complete this key informant interview will be compensated an additional \$50 by check for their time and insights.

## Statistical Plan

### **6.1 Sample size Determination:**

Given that this is a pilot study, our goal is to determine the effect size of the intervention to determine the statistical power needed for subsequent larger studies. Based on our assessment of the recruitment pool and resources available through the award, we will enroll 25 patients in each arm ( $n = 50$ ) with anticipated 20% dropout rate over 6 months for an estimated final analysis sample of 40 patients. Based on previous studies, we can anticipate a mean systolic blood pressure change of 7.6 mmHg, and a standard deviation of 15 mm Hg, for an effect size of 0.51. An effect size of  $< 0.3$  will be considered insignificant.

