## Study Summary

Title	A Clinic-Based Case Manager Administered Telephone Intervention to Reduce Cardiovascular Disease Risk in Persons Living with HIV
Short Title	SWOBI-CVD
Protocol Number	Pro00085562
Phase	Phase 3
Methodology	Randomized Controlled Trial
Study Duration	24 months
Study Center(s)	Single-center
Objectives	To assess the impact of telephone-based case manager administered interventions in improving ASCVD risk factor outcomes among HIV-infected clinic patients.
Number of Subjects	50
Diagnosis and Main Inclusion Criteria	Patients diagnosed with HIV and either hyperlipidemia or hypertension
Duration of administration	24-weeks
Statistical Methodology	Generalized linear mixed regression models will be used to assess the changes in systolic blood pressure and LDL-c over the period of the intervention, accounting for repeated measurements within subjects as well as clustering of subjects within providers. Bivariable and multivariable analyses will be conducted for all covariates. To test for the effect of time on the differences in SBP and LDL-c between the groups, we will fit a constrained longitudinal data model (cLDA).  We will fit models with time as a categorical variable (based on the time of outcome measure collection) and as a continuous variable, to determine the best model fit.

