### **6.2 Statistical Methods**

Data on the outcome variables (blood pressure, non-HDL/LDL, 10-year ASCVD risk score) for each arm will be collected at weeks 0, 6, 12 and 18 months. Summary statistics of the study cohort will be reported for every interim timepoint. Generalized linear mixed regression models will be used to assess the changes in systolic blood pressure and LDL-c over the period of the intervention. Models will be fit with an interaction term to account for the difference of differences (DID) at each timepoint in the study (on intervention and post intervention timepoints to assess durability of the intervention's effect) to assess the treatment effect between the two arms. The p-value of the interaction term will serve as significance testing for the difference between the outcome value difference of the two study arms. The same technique will be used for the secondary analysis of ASCVD risk scores.

Missing data will be handled as follows:

- Variables with more than 30% missingness will be dropped from the analysis regardless of reason
- Variables with less than 30% missingness will be evaluated by individual observations. If the data point is determined to be missing at random, then values will be imputed in its place using multiple dataset imputation methods. If the data point is determined to be not missing at random, then the observation of missingness will be reported in the summative reporting after the reasons for the patterns of missingness have been determined. The missing values will then be imputed by the predicted linear regression model.
- Any observations without data from the intervention completion (week 24) timepoint will be excluded from the analysis

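### Section 6.1 labels the effect from a point estimate against 0.3 and uses it to power later studies, with no interval planned; the 95% half-width is about 0.64 SD

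*Combined protocol and SAP*

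**What the plan says.** Section 6.1 gives the pilot's purpose: "our goal is to determine the effect size of the intervention to determine the statistical power needed for subsequent larger studies". It plans 25 patients per arm and 20% dropout over 6 months, for an "estimated final analysis sample of 40 patients". It anticipates a "mean systolic blood pressure change of 7.6 mmHg, and a standard deviation of 15 mm Hg, for an effect size of 0.51", and says that an effect size below 0.3 "will be considered insignificant". It does not say whether that word is meant statistically or clinically, or whether 15 mmHg is the SD of a change or of a single reading.

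On the analysis, section 6.2 says: "Models will be fit with an interaction term to account for the difference of differences (DID) at each timepoint in the study". It continues: "The p-value of the interaction term will serve as significance testing". The Study Summary describes mixed models "accounting for repeated measurements within subjects as well as clustering of subjects within providers" and also names a constrained longitudinal model (cLDA). Neither document part states a significance level, a confidence level, or a confidence interval for the treatment effect.

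**The concern.** Section 6.1 gives the effect estimate two jobs. It is compared with a fixed cutoff to decide whether the effect is called insignificant, and it informs the power of later studies. Both jobs need to know how far the estimate may lie from the truth, and the plan asks for no measure of that.

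Two things are at stake. The pilot report could dismiss an intervention that works as well as the investigators hope, because the estimate happened to fall under 0.3. And the next trial could be sized far from what is needed if the estimate is taken at face value.

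**Working it through.** **Inputs from section 6.1.** Anticipated difference 7.6 mmHg; SD 15 mmHg; 25 enrolled per arm; 20% dropout; cutoff 0.3. Section 3.1 gives 1:1 allocation.

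**Assumptions, not in the documents.** Equal dropout by arm; two-sided 0.05 and 95% intervals; the correlations used below; no allowance for clustering by provider.

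**The plan's own figures.** 7.6/15 = 0.507, which matches 0.51. 50 × 0.80 = 40 analysed, so 20 per arm. The cutoff in mmHg is 0.3 × 15 = 4.5.

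**Precision, with 15 mmHg as the SD of the analysed outcome.**
- SE = 15 × √(2/20) = 4.74 mmHg.
- Half-width = t(0.975, 38 df) × SE = 2.024 × 4.74 = 9.60 mmHg; 9.60/15 = 0.64 SD.
- With no dropout at all (25 per arm) it would still be 8.53 mmHg, or 0.57 SD.

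**How often the 0.3 label goes wrong.** If the true effect is 0.507, the chance that the estimate is below 0.3 is Φ((4.5 − 7.6)/4.74) = 0.257; the noncentral t gives 0.256. That is about 26%.

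**What an estimate just under 0.3 shows.** An observed 0.29 is 0.29 × 15 = 4.35 mmHg. Its 95% interval is 4.35 ± 9.60, or about −5.3 to 14.0 mmHg, which contains 7.6. The upper limit falls below 7.6 only if the observed difference is below 7.6 − 9.6 = −2.0 mmHg, that is, only if the intervention arm does worse.

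**If 15 mmHg is the SD of a single reading.** Let r be the correlation between baseline and week 24. The difference-of-differences SE is 4.74 × √(2(1 − r)). The baseline-adjusted SE, an approximation to cLDA, is 4.74 × √(1 − r²), with t(37) = 2.026. The cutoff stays at 4.5 mmHg and the true effect at 7.6 mmHg.

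| r | Analysis | Half-width, mmHg (SD) | Chance of estimate below 0.3 | p if 7.6 is observed |
|---|---|---|---|---|
| 0.3 | Difference of differences | 11.36 (0.76) | 29% | 0.18 |
| 0.5 | Difference of differences | 9.60 (0.64) | 26% | 0.12 |
| 0.7 | Difference of differences | 7.44 (0.50) | 20% | 0.045 |
| 0.3 | Baseline-adjusted | 9.17 (0.61) | 25% | 0.10 |
| 0.5 | Baseline-adjusted | 8.32 (0.55) | 23% | 0.07 |
| 0.7 | Baseline-adjusted | 6.86 (0.46) | 18% | 0.031 |

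Every half-width exceeds 0.3 SD. In every row an observed 4.35 mmHg leaves 7.6 inside the interval; the narrowest upper limit is 4.35 + 6.86 = 11.2. The p-value for an observed 7.6 mmHg does depend on the assumption: it is 0.12 when 15 is the SD of the analysed outcome, but below 0.05 in both r = 0.7 rows.

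**Sizing the next trial from the point estimate.** This assumes a true 0.507, 15 mmHg as the SD of the analysed outcome, a two-sample t-test and 80% power. The quartiles of the estimate are 0.294 and 0.732. The approximation n = 2(1.96 + 0.84)²/d² gives about 182, 62 and 30 per arm at d = 0.294, 0.507 and 0.732. The t-test calculation gives 183, 63 and 31. So the middle half of pilots would size the next trial at between 183/63 = 2.9 times and 31/63 = 0.5 times what is needed. At 31 per arm, power for 0.507 is about 50%.

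No such calculation is possible for LDL-c, because the plan gives no SD for it.

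**The case against.** **The 0.3 rule and the p-value can coexist.** A reader might infer that 6.1 contradicts 6.2, since estimates of 4.5 to 9.6 mmHg are not insignificant under 6.1 yet have p above 0.05 under 6.2. The documents do not support that as a necessary reading. Section 6.1 never says that 0.3 or more is significant or sufficient, so 0.3 may be a floor beside the p-value. The range itself also holds only if 15 mmHg is the SD of the analysed outcome. What remains is an undefined word.

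**Passing 0.3 triggers nothing.** A reader might also infer that a useless intervention would succeed about one time in six, because under a true zero the estimate reaches 0.3 in about 17% of pilots. No decision in the documents depends on reaching 0.3. Significance rests on 6.2, where a null effect would be declared favourable in about 2.5% of pilots at the assumed level.

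**The interval is available anyway.** The planned model yields a standard error, and nothing forbids reporting an interval. This stands in part: no data are lost. But the plan names only a p-value, and the 0.3 rule refers to no interval.

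**Later designers may not plug in the raw estimate.** True. Section 6.1 does not say the estimate will be used unadjusted, so the sizing figures are conditional on that use.

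**It is a pilot.** Its size was set by the recruitment pool and resources, and that is not criticised. The point is what may be concluded from an estimate of this precision.

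**Conclusion.** The point holds in a limited form. Section 6.1 applies a cutoff to a point estimate whose 95% half-width is about 9.6 mmHg (0.64 SD), and intends that estimate to inform later power, with no interval planned. An effect of the size the investigators anticipate would be called insignificant in about 26% of pilots, or 18 to 29% across the single-reading cases. An estimate just under 0.3 would not exclude 7.6 mmHg in any case examined. Direct use of the estimate for sizing could put the next trial at about three times, or half, the number needed.

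These figures rest on equal dropout, two-sided 0.05, no provider clustering and, for the headline values, 15 mmHg being the SD of the analysed outcome. The consequence within this trial is a misleading label, not a wrong decision. It is worth correcting because the correction costs almost nothing.

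**What to change.** In section 6.1, replace the goal sentence and the 0.3 sentence with:

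> The pilot will estimate the week-24 between-arm difference with its 95% CI; no efficacy or futility conclusion will be drawn from the point estimate alone. The next trial will be sized on a pre-stated clinically relevant difference, using the pilot SD (with its uncertainty), baseline correlation and dropout, with the pilot CI as supporting information.

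State whether 15 mmHg is the SD of change or of a single reading, then give the expected half-width (about 9.6 mmHg if it is the SD of the analysed outcome).

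If 0.3 is kept as the smallest important effect, say so, judge it against the 95% CI, and say that at this size the result will usually be inconclusive. If the true effect is 0.51, the interval lies wholly above 0.3 in about 10% of pilots and wholly below it in about 0.4%, which leaves about 90% undecided.

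In section 6.2, state the significance level and report the 95% CI beside the interaction p-value.

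**Cost.** A few lines of text; no extra patients, visits or data, since the interval comes from the model already planned. The stated aim becomes more modest. The pilot SD is not exact either: with 38 df, an observed 15 mmHg has a 95% interval of about 12.3 to 19.3 mmHg, which scales the next sample size by about 0.67 to 1.66. That is why the wording carries its uncertainty.

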### **6.2 Statistical Methods**

Data on the outcome variables (blood pressure, non-HDL/LDL, 10-year ASCVD risk score) for each arm will be collected at weeks 0, 6, 12 and 18 months. Summary statistics of the study cohort will be reported for every interim timepoint. Generalized linear mixed regression models will be used to assess the changes in systolic blood pressure and LDL-c over the period of the intervention. Models will be fit with an interaction term to account for the difference of differences (DID) at each timepoint in the study (on intervention and post intervention timepoints to assess durability of the intervention's effect) to assess the treatment effect between the two arms. The p-value of the interaction term will serve as significance testing for the difference between the outcome value difference of the two study arms. The same technique will be used for the secondary analysis of ASCVD risk scores.

Missing data will be handled as follows:

- Variables with more than 30% missingness will be dropped from the analysis regardless of reason
- Variables with less than 30% missingness will be evaluated by individual observations. If the data point is determined to be missing at random, then values will be imputed in its place using multiple dataset imputation methods. If the data point is determined to be not missing at random, then the observation of missingness will be reported in the summative reporting after the reasons for the patterns of missingness have been determined. The missing values will then be imputed by the predicted linear regression model.
- Any observations without data from the intervention completion (week 24) timepoint will be excluded from the analysis

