### **6.3 Subject Population(s) for Analysis**

All randomized subjects with at least partial outcome data for the baseline and week 24 timepoints will be included in the analysis, regardless of missingness of the post-intervention timepoints.

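### Section 6.2 does not carry over the constrained-baseline model (cLDA) or the provider clustering named in the Study Summary, and on its natural reading it is the less precise analysis

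*Combined protocol and SAP*

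**What the plan says.** The analysis is described in two places.

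- **Study Summary, Statistical Methodology.** Generalised linear mixed models will be used for SBP and LDL-c, "accounting for repeated measurements within subjects as well as clustering of subjects within providers". To test the effect of time on the group differences, "we will fit a constrained longitudinal data model (cLDA"). Time will be fitted both as categorical and as continuous, to find the better fit.
- **Section 6.2.** Generalised linear mixed models are named again, but the treatment effect is described differently: "Models will be fit with an interaction term to account for the difference of differences (DID) at each timepoint in the study". The test is then defined: "The p-value of the interaction term will serve as significance testing for the difference between the outcome value difference of the two study arms". There is no mention of the cLDA, of a common baseline mean, or of providers. Nor does the section say whether an arm main effect (a baseline difference between arms) is fitted.

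Neither place says which model is primary.

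The sizing comes from section 6.1. On enrolment it says "we will enroll 25 patients in each arm". On attrition it plans "with anticipated 20% dropout rate over 6 months for an estimated final analysis sample of 40 patients". On the expected effect it says "we can anticipate a mean systolic blood pressure change of 7.6 mmHg, and a standard deviation of 15 mm Hg, for an effect size of"; the value it then states is 0.51. Section 6.1 gives the pilot's goal as determining the effect size, so that later studies can be powered, and treats an effect size below 0.3 as insignificant. Section 6.3 defines the analysis set: "All randomized subjects with at least partial outcome data for the baseline and week 24 timepoints will be included in the analysis".

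**The concern.** An analyst working from section 6.2 alone would most likely fit arm, time and arm-by-time, and report the interaction. At week 24 that is the mean change in one arm minus the mean change in the other. An analyst working from the Summary would fit a cLDA, which sets the two baseline means equal, as randomisation justifies, and so adjusts for baseline. The two give different estimates and standard errors from the same data. Including or leaving out a provider effect adds a further fork.

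The pilot's main product is an effect size with its uncertainty. If the less efficient model is used, the interval around that effect size is wider than the collected data require. If the model is chosen after the data are seen, the reported effect size is not pre-specified.

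**Working it through.** **Plan's own figures.** 7.6/15 = 0.507, which rounds to the stated 0.51. 50 × (1 − 0.20) = 40, or 20 per arm. Both reproduce. Section 6.1 states no power or alpha, so there is no power figure to reproduce.

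**Inputs**
- n = 20 per arm (section 6.1, with dropout assumed equal in the two arms).
- SD 15 mmHg (section 6.1). The text does not say whether this is the SD at a visit or the SD of change, so both are shown.
- rho, the correlation between baseline and week 24: not in the documents. Values of 0.3, 0.5 and 0.7 are assumed.
- Equal variances at the two visits, and two-sided 95% intervals with t(38) = 2.024: assumed.
- Baseline and week-24 data present for everyone analysed (close to what section 6.3 requires).

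**Formulas for the week-24 arm difference**, with sigma the visit SD
- Unconstrained difference of differences (DID): variance = (2/n) × 2 sigma² (1 − rho).
- cLDA: variance = (2/n) × sigma² (1 − rho²).
- Ratio cLDA/DID = (1 + rho)/2, so the DID variance is larger by 2/(1 + rho).

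Generalised least squares with all four visits, under compound symmetry and under AR(1), gives the same ratio at week 24.

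| Assumed rho | Variance ratio cLDA/DID | Variance cut | SE cut | DID variance inflation |
|---|---|---|---|---|
| 0.3 | 0.65 | 35% | 19% | 1.54 |
| 0.5 | 0.75 | 25% | 13% | 1.33 |
| 0.7 | 0.85 | 15% | 8% | 1.18 |

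**Half-widths if 15 is the visit SD.** SE(DID) = 15 × √(2(1 − rho)) × √(2/20). SE(cLDA) = 15 × √(1 − rho²) × √(2/20). Each is multiplied by 2.024.

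| rho | SE, DID → cLDA (mmHg) | 95% half-width, DID → cLDA (mmHg) |
|---|---|---|
| 0.3 | 5.61 → 4.52 | 11.4 → 9.2 |
| 0.5 | 4.74 → 4.11 | 9.6 → 8.3 |
| 0.7 | 3.67 → 3.39 | 7.4 → 6.9 |

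**Half-widths if 15 is the SD of change.** SE(DID) = 15 × √(2/20) = 4.74 at every rho, a half-width of 9.6 mmHg. Multiplying the SE by √((1 + rho)/2) gives 3.82, 4.11 and 4.37, and half-widths of 7.7, 8.3 and 8.9 mmHg at rho 0.3, 0.5 and 0.7.

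**Small-sample allowance.** The formulas treat the baseline slope as known. Estimating it with 40 patients inflates the adjusted variance by about 1 + 1/(40 − 4) = 1.028, so the ratios become about 0.67, 0.77 and 0.87. A simulation of 200,000 two-arm trials of 20 per arm, with ANCOVA at week 24, gave 0.667, 0.769 and 0.874. At rho 0.5, 40 patients analysed with the constraint are then worth about 40/0.77 = 52 analysed without it.

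**Where the extra variance comes from.** For a chance baseline difference d, the expected DID shifts by (1 − rho)d in magnitude. With visit SD 15 and 20 per arm, the SD of d is 15 × √(2/20) = 4.74 mmHg. At rho 0.5 a one-SD imbalance therefore moves the DID by 2.4 mmHg, about half of the 0.3 × 15 = 4.5 mmHg that section 6.1 treats as its floor. This is the same loss seen another way: 16.9 (cLDA variance) + 0.5² × 22.5 = 22.5 (DID variance).

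**The case against.** The strongest reply is that the documents do not contradict each other. Section 6.2 never says that the baseline is unconstrained and never says that an arm main effect is fitted. A cLDA also estimates its effects through arm-by-time terms and simply omits the arm term at baseline. The two texts can therefore be read as one mixed model whose constrained form is named only in the Summary. This stands: a reader might infer that section 6.2 prescribes an unconstrained model, but that is an inference from its wording about a difference of differences. It does not remove the point, because if the cLDA is meant, section 6.2 needs the same edit.

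Three other tempting readings go too far.

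- *A third of the precision is lost.* A third is the variance cut at rho = 1/3 only. It is not an upper bound (the limit is 50% at rho = 0), and it is not on the interval scale, where the cut at rho = 1/3 is 18%. No rho is given.
- *The DID is biased by chance imbalance or regression to the mean.* Over randomisations both estimators are unbiased. The sensitivity to imbalance is the source of the extra variance, not a second harm.
- *ANCOVA of the week-24 value would serve equally well.* It is close to the cLDA at week 24, but it does not supply the month 12 and month 18 contrasts that section 6.2 also wants.

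**Conclusion.** The concern holds as a matter of efficiency and pre-specification, not of validity. The Summary names a cLDA and provider clustering, section 6.2 names neither, and nothing says which model yields the reported effect.

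If section 6.2 is followed on its natural reading, the standard error at week 24 is larger than it need be. Constraining the baseline would cut it by about 19%, 13% or 8% at rho 0.3, 0.5 or 0.7, and slightly less once the slope is estimated. In mmHg the half-width narrows by roughly 0.6 to 2.2 if 15 is the visit SD, and by roughly 0.7 to 1.9 if it is the SD of change.

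These sizes rest on the assumed rho, equal variances and 20 complete pairs per arm. They are for SBP only. The documents give no figures from which to size the gain for LDL-c or the effect of provider clustering. If the sponsor already intends the cLDA, the precision loss does not arise and only the omission from section 6.2 remains. The change is worth making either way, before any outcome data are compared by arm.

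**What to change.** - In section 6.2, name the Summary's cLDA as the single primary model for SBP and for LDL-c: a common baseline mean (no baseline arm term), with arm-by-time terms at the post-baseline visits only.
- Report the week-24 arm difference from that model, with its 95% interval, as the effect. Report the later visits from the same model as durability contrasts.
- Keep an unconstrained difference of differences, if wanted, as a sensitivity analysis only.
- Make the Study Summary and section 6.2 agree on whether a provider effect is in the model.
- In section 6.1, say whether 15 mmHg is the SD at a visit or the SD of change, so that the expected precision can be stated.

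The cost is wording only. Baseline values are already collected, the Summary already endorses the model, and randomisation justifies the constraint. The statistical price is the small allowance for estimating the baseline slope, about 3% of the variance at 40 patients.

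### Values judged not missing at random are filled by a regression prediction that is valid only under missing at random, with uncertainty and arm left unspecified

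*Combined protocol and SAP*

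**What the plan says.** All references are to the combined protocol and SAP.

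Section 6.2 applies imputation to variables below a missingness threshold: "Variables with less than 30% missingness will be evaluated by individual observations". A point judged missing at random goes to one route: "then values will be imputed in its place using multiple dataset imputation methods". A point judged not missing at random goes to another. Its missingness is reported once the reasons for the pattern have been worked out, and then: "The missing values will then be imputed by the predicted linear regression model".

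Two provisions limit the reach of the fill. Section 6.2 adds: "Any observations without data from the intervention completion (week 24) timepoint will be excluded from the analysis". Section 6.3 keeps randomised participants with "at least partial outcome data for the baseline and week 24 timepoints will be included in the analysis", and does so "regardless of missingness of the post-intervention timepoints".

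The treatment effect is read from an arm-by-time interaction, covering "the difference of differences (DID) at each timepoint in the study", including the visits after the intervention. Section 5.10 gives durability as the purpose of those visits. The Study Summary also plans a constrained longitudinal model.

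No section names the predictors in the regression, says whether arm is among them, says whether residuals are drawn or the fill repeated, or plans a sensitivity analysis for data not missing at random.

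**The concern.** A regression fitted to observed values predicts the missing ones without bias only if, given the predictors, missing and observed values follow the same distribution. That is missing at random. The branch therefore relies on the assumption it was created to reject, and the stronger method goes to the easier case. The sorting is also weak: recorded withdrawal reasons (Section 4.4) can inform it, but observed data cannot settle it point by point.

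Two silences then decide what goes wrong.

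- **Uncertainty.** Only the other branch names multiple imputation, so the plain reading is one predicted value analysed as if measured. That makes standard errors too small.
- **Arm.** If arm is not a predictor, filled values are pulled towards a common mean and a real effect shrinks.

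Section 6.1 says the pilot exists to estimate an effect size for later trials and treats anything below 0.3 as insignificant. Distorted durability estimates would feed into that use.

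**Working it through.** **Inputs from the plan (Section 6.1).** 7.6 / 15 = 0.507, the stated 0.51. 50 × (1 − 0.20) = 40 analysed, so 20 per arm. Both figures reproduce.

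**Assumptions not in the documents.** Correlation 0.5 between any two visits; random-intercept model with arm by time over four visits; no provider clustering; two-sided 5% test; 12- and 18-month values removed at the stated rates; fill regressed on baseline, 6 months and, where stated, arm. All rates are kept below 30%, where Section 6.2 imputes. Results are simulated, with 1,500 to 8,000 trials per scenario.

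**Complete-data benchmark.** Within-person variance = 225 × (1 − 0.5) = 112.5. SE of the difference of differences = √(4 × 112.5 / 20) = 4.74 mmHg.

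**(a) Arm in the fill, values missing completely at random, 12-month contrast, no true effect**

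| Missing | 10% (4 of 40) | 20% (8) | 27.5% (11) |
|---|---|---|---|
| Reported / true SE, all predicted | 4.60 / 4.93 | 4.46 / 5.14 | 4.36 / 5.29 |
| False positives, all predicted | 6–7% | 8–9% | 10–11% |
| Half predicted, rest multiply imputed | 5.4% | 6.9% | 7.6% |
| Quarter predicted, rest multiply imputed | 5.2% | 5.2% | 5.5% |
| Observed outcomes only, no fill | 4.3% | 5.1% | 4.9% |

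The reported SE falls as more data go missing, while the true one rises. With the constrained baseline of the Study Summary the rates are 7.1%, 9.2%, 11.4% (all); 5.9%, 6.5%, 7.1% (half); and 5.7%, 5.0%, 5.9% (quarter). Correlations of 0.3 and 0.7 barely change the all-predicted rates.

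**(b) Arm left out.** The false-positive rate holds (5.1%, 4.7%, 5.0%), but a true 7.6 mmHg becomes 7.1, 6.7 and 6.3. At 20% missing the observed part contributes 0.80 × 7.6 = 6.08. The simulated 6.66 means the filled fifth carries only (6.66 − 6.08) / 0.20 = 2.9 mmHg.

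**(c) Values truly not missing at random, arm in the fill.** The bias in the contrast is (missing fraction × hidden shift) in the intervention arm minus the same product in the control arm. Suppose the whole 7.6 mmHg is lost in missing intervention-arm values and there is no shift in controls:

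| Missing per arm | 10% | 20% | 25% |
|---|---|---|---|
| Overstatement, mmHg | 0.10 × 7.6 = 0.76 | 0.20 × 7.6 = 1.52 | 0.25 × 7.6 = 1.90 |
| Overstatement / 15 | 0.05 SD | 0.10 SD | 0.13 SD |
| True effect | 6.84 | 6.08 | 5.70 |
| Effect reported | 7.6 | 7.6–7.7 | 7.6 |
| 95% interval coverage | 93% | about 90% | 87–88% |

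If the same shift applies in both arms with equal missingness, it cancels: the estimate stays at 7.6 to 7.7 against 7.6. Coverage is then still only about 93%, 91% and 90%, so most of the shortfall in the table comes from the understated SE.

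**Reach at week 24.** With week-24 systolic pressure observed, filling later visits leaves its point estimate unchanged in the unconstrained model. Its interval narrows a little through the pooled residual variance (false positives 5.6%, 6.5%, 7.0% if all later values are predicted; 5.1–5.4% if half). In the constrained model the estimate can move slightly: at 27.5% missing, the changes had SD 0.15 and a maximum of 0.6 mmHg over 60 trials.

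Section 6.3 asks only for partial outcome data. If the exclusion in Section 6.2 is read per participant, someone with week-24 systolic pressure but no LDL stays in, and LDL, a primary outcome (Section 2.1), is filled. At 5%, 10% and 20% filled, all-predicted false positives are 5.7%, 6.1% and 7.8%. With arm omitted, an effect of 0.51 SD becomes 0.48, 0.45 and 0.40.

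**The case against.** Several objections have force.

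- **A reader might infer that any departure from missing at random biases the treatment effect.** The planned estimand is a between-arm difference of differences, so it does not: equal shifts with equal missingness cancel. Bias needs the arms to differ. Nothing in the plan makes them alike (one arm receives 12 calls, the other pamphlets only), but nothing shows that they differ.
- **A reader might infer that the week-24 systolic result is invalid.** The week-24 exclusion prevents that, apart from the small effects shown. If the exclusion is read per outcome, a missing week-24 LDL is dropped rather than filled. Even on the participant reading, Section 5.7 has staff draw a lipid panel when no timely routine one exists, so such gaps should be uncommon.
- **A reader might infer a false-positive rate near 10%.** That needs every missing value to be judged not missing at random and more than 20% missing. The documents give neither that share nor the 12- and 18-month missingness.
- **The plan does require this missingness to be explained and reported.** That transparency is worth keeping, and it is wrong to say the issue is ignored. But reporting does not change the filled value.

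Single prediction without a residual draw is the plain reading, not something the plan states. The contradiction in the branch stands on either reading.

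**Conclusion.** The rule is wrong as written, not merely short of detail: it uses a missing-at-random method for values it has declared not missing at random, and no other section repairs this. It should be fixed, though the practical reach is modest. The exposed results are the durability contrasts at 12 and 18 months and, on one reading, an occasional week-24 LDL value.

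The size depends on the undefined details. With arm included and no uncertainty, false positives at 12 months run from near nominal (a quarter predicted) through about 5–8% (half) to 10–11% (all, at 27.5% missing). With arm omitted, 7.6 mmHg shrinks to between 7.1 and 6.3. An overstatement of 0.05 to 0.13 SD requires the whole effect to be lost in missing intervention-arm values only. All of these rest on the assumed correlation, missingness and random-intercept model.

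**What to change.** 1. In Section 6.2, delete the point-by-point sorting and the regression-prediction step.
2. State that the planned likelihood mixed model on observed outcomes, with no imputed outcomes, is primary and assumes missing at random.
3. Keep the reporting of reasons, and add missingness by arm and visit.
4. Add one sensitivity analysis: multiple imputation with arm in the imputation model, arm-specific shifts over a pre-stated range, combined by Rubin's rules. Include shifts in the intervention arm only, for example 0 to +7.6 mmHg for systolic pressure. The sponsor should state the LDL range, since the documents give none.

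The shift must be arm-specific. In scenario (c) at 10% and 20% missing, shifting the intervention arm alone by 7.6 gives 6.9 and 6.2 against truths of 6.8 and 6.1, with 95–96% coverage. Shifting both arms gives 7.6 and 7.7 and misses the problem.

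The SAP should say that the primary model alone does not remove the bias in (c); only the shifted analysis shows it.

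The cost is SAP wording, one modest analysis and wider durability intervals. At 20% missing the SE is about 5.1 instead of 4.5 mmHg, or 4.5 instead of 3.9 with the constrained baseline. The smaller figures were understated, so little real precision is lost. The 30% rule and the choice of analysis population are separate matters.
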